Funding for this project has been provided through the 2014 *IADR/Unilever Social Entrepreneur Approach to Change Oral Health Behaviour Research Award*, administered by the International Association for Dental Research (IADR) and sponsored by Unilever (http://www.iadr.org/).

Location of study

The study will be administered from the Oral Health Services Research Centre in Cork University Dental School & Hospital. Patients will be seen by their General Dental Practitioners (GDPs) in the GDP surgeries. Text messages will be sent from the UK-based Text Magic service (https://www.textmagic.com/).

Aim of study

This project aims to investigate the effectiveness of an electronic-based caries risk assessment (Cariogram) with a personalised educational approach adopting personalised marketing for caries prevention in lower socioeconomic groups.

Specific objectives

The specific objectives are:

- 1. To assess the influence on seven caries risk factors:
 - frequency of fermentable-carbohydrate intake (sugars)
 - amount of plaque present
 - bacterial counts

 - ♦ lactobacilli (LB)
 - use of fluorides
 - salivary flow
 - salivary buffering capacity
- 2. To assess whether there is an increase in patient engagement with the dentist
- 3. To assess the prevalence and distribution of the risk factors indicated along with past caries experience and systemic diseases and conditions such as cardiovascular

- disease, diabetes and obesity
- To assess the knowledge, behaviour and patient satisfaction relating to 4. personalised caries prevention.

Investigator and research personnel

Role	Name	Address	
Principal	[name]	Restorative Dentistry, University	
Investigator		Dental School & Hospital, University	
		College Cork	
Co-investigator	[name] BDS,	Oral Health Services Research Centre,	
	MFGDP(UK), MDPH	University Dental School, Cork	
	Senior Dental Surgeon	HSE South Cork ISA	
Co-investigator	[name]	Oral Health Services Research Centre,	
	BEd(Japan),	University Dental School, Cork	
	DDS(Japan), MDPH		
Laboratory	[name]	Oral Health Services Research Centre,	
Technician		University Dental School, Cork	
Statistician	To be recruited		
Programmer	[name]	School of Computer Science and	
	Undergraduate student,	Information Technology, University	
	supervised by [name] Cork	
	[name]		

Ethics approval

This project has had the approval of the Clinical Research Ethics Committee of the Cork Teaching Hospitals.

Preparatory work

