An estimated 200 medical-card (i.e. proxy for low socioeconomic status) patients will be recruited from approximately ten general dental surgeries in Ireland. The inclusion criteria are (i) 19–70 years of age, (ii) medical-card holder, (iii) \geq 20 teeth present, (iv) not pregnant, (v) ability to use text messaging and (vi) willingness to participate in the project.

Training module for dental professionals

[name] and [name] explained the project protocol to the participating dental professionals, and will train them in the study procedures. [name] has worked extensively with the Cariogram. The dental professionals are being calibrated for DMFT/DMFS and plaque index. This training is being carried out in the OHSRC.

Baseline examination

At the first appointment in the general dental surgery, the study will be explained and informed consent will be obtained prior to examination. The dental practitioner will interview the patient (fluoride use, related systemic diseases / conditions), collect saliva samples (determine salivary flow rate, salivary buffer capacity, bacteriological tests, CRT® Ivoclar Vivadent, Liechtenstein), examine (past caries experience, plaque amount) and provide a questionnaire and a dietary record form for the subject. The CRT® agar culture, history form including fluoride use and systemic diseases and oral examination form will be sent to the OHSRC within a day from the dental surgery by car.

Informed consent

If the patient meets the inclusion criteria listed above, they will be invited by the general dental surgeon to read the information sheet for patients. If they agree to participate in the project, they must sign the informed consent form.

Past caries experience

Past caries experience will be recorded for each tooth surface. Recording codes are outlined in Appendix 5 of this protocol.

Plaque amount

The Plaque Index (PI), according to Silness and Löe (1964) will be used. Recording codes are outlined in Appendix 5 of this protocol.

Fluoride use

Relevant information on fluoride use will be obtained through patient interviews. The patient will be asked:

- if the patient uses fluoridated water,
- if the patient uses fluoridated tooth paste,
- if the patient uses additional fluoride measures such as rinses and varnishes frequently,
- if the patient uses additional measures such as rinsing and varnishes, infrequently.

Related systemic diseases

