The relevant information on systemic diseases will be obtained by patient interviews only. The patient will be asked whether he/she suffers from diseases / conditions such as:

- autoimmune diseases, like Sjögren's syndrome
- diabetes mellitus
- anorexia nervosa
- visually impaired
- any manual dexterity which might cause them difficulties with cleaning their teeth properly.
- any disease, which requires continuous medication that, for example, affects their saliva secretion. Details of any concomitant medications will be recorded.
- any condition requiring radiation to the head-neck region

Saliva tests

The general dental surgeon will collect saliva samples in a standardised format,

from participating patients to determine salivary flow rate, saliva buffering capacity and bacteriological testing. Details of saliva sampling procedures are outlined in Appendix 3 of this protocol.

The laboratory technician in the OHSRC will incubate and read the CRT® slides in accordance with the manufacturer's instructions.

Dietary record/Questionnaire

The patient will be provided with the 3-day dietary record and the study questionnaire, along with a stamped, addressed envelope for return of completed documents to the OHSRC.

Randomisation

The subjects will be stratified for "chance to avoid new cavities" by quartiles (0–20%, 21–40%, 41–60%, 61%–100%) and randomly allocated to Test or Control group by the statistician.

Intervention

A report of their caries risk assessment, along with their output chart as generated by Cariogram, will be sent by post to the subjects in the Test group. The subjects in the Control group will be sent only general information (not generated by Cariogram) on caries prevention, also by post. A €20 voucher will be sent to all subjects as a token of appreciation for participating in the study.

Once weekly for 24 weeks, the Test group will receive personalised oral health text messages on caries prevention while the Control group receives non-personalised text messages offering general oral healthcare advice.

Table 1 shows how to calculate numbers of text messages allocated to each risk sector for the Test group. All subjects in the Control group will receive the same six non-personalised text messages for each risk sector. All oral health messages are evidence-based (Levine and Stillman-Lowe 2009).

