Table 1. How to calculate numbers of text messages of each sector. Using the example in Figure 1, over the 24 week study period, the EPES will send this patient nine text messages on bacteria (33/84), three text messages on diet (11/84), two text messages on circumstances (7/84) and nine text messages on susceptibility (33/84).

Sector (Risk Factor / Risk Indicator)	Percentage contribution calculated with the Cariogram chart (%)	Proportion contribution of each sector to the overall calculated risk (%)	Number of texts on each sector to be sent text messages
Bacteria (plaque and mutans streptococci)	33	39	9
Diet (content and frequency)	11	13	3
Circumstances (previous caries experience, co-exiating diseases)	7	8	2
Susceptibility (available fluorides, saliva properties)	33	39	9
Total of the four sectors	84	100	24
"Chance to avoid new cavities"	16		
Total of the five sectors	100		

Follow-up examination

At the second appointment, six months after the baseline examination, the same data collection procedures as at baseline (except the taking of informed consent) will be followed. After the six-month assessment, both Test and Control group subjects will be sent their baseline and follow-up output charts and their personalised caries prevention advice as generated by Cariogram, along with their reward for completing the study (€30 voucher), by post from the OHSRC.

Data analysis

[name] will enter baseline and six-month follow-up data into the Cariogram software programme and generate Cariogram reports for each patient at each timepoint.

The data will be analysed using a statistical package (SPSS/SAS) by [name] with the aid of a statistician. The average of "chance to avoid new cavities" as measured by Cariogram as well as the seven risk factors before and after the intervention between the test and control groups will be compared using a two-sample two-sided t-test. In addition, the measured risk factors/indicators and questionnaires results will be analysed for the third and fourth research objectives.

Infection control

Infection control in accordance with the Dental Council Ireland guidelines, (http://www.dentalcouncil.ie/g_crossinfection.php) and Cork University Dental School and Hospital will be adhered to.

Potential risks and benefits to participants

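### Surgery is left out of both the allocation and the stated comparison, which costs some avoidable precision but causes no bias

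*Protocol*

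**What the plan says.** The Randomisation section names one stratification factor: "The subjects will be stratified for 'chance to avoid new cavities' by quartiles (0–20%, 21–40%, 41–60%, 61%–100%) and randomly allocated to Test or Control group". The statistician makes the allocation. Under Subject recruitment, "patients will be recruited from approximately ten general dental surgeries in Ireland", and Location of study adds: "Patients will be seen by their General Dental Practitioners (GDPs) in the GDP surgeries".

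Much of the information behind the Cariogram score is gathered in those surgeries. Under Baseline examination, "The dental practitioner will interview the patient (fluoride use, related systemic diseases / conditions), collect saliva samples", and the same practitioner records past caries and plaque. At six months "the same data collection procedures as at baseline (except the taking of informed consent) will be followed".

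The protocol also contains steps that limit differences between surgeries. Under Training module, "The dental professionals are being calibrated for DMFT/DMFS and plaque index". Under Saliva tests, "The laboratory technician in the OHSRC will incubate and read the CRT® slides in accordance with the manufacturer's instructions". Diet records and questionnaires are posted to the research centre, and Cariogram entry is central.

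For the analysis, the Data analysis section says that the score and the risk factors before and after the intervention "between the test and control groups will be compared using a two-sample two-sided t-test". The Summary describes the same test on the average change. Neither place mentions surgery.

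**The concern.** Surgery is the unit through which patients are recruited, seen and scored. Surgeries may differ in how interviews are conducted, how saliva is collected, how strictly plaque and caries are scored, and how patients' scores move over six months. The section on risks and benefits itself expects dentists to learn from taking part and caries management in the surgeries to improve, and that could happen unevenly.

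With allocation balanced on score band alone, one arm can by chance receive clearly more of a given surgery's patients. With no surgery term in the comparison, any between-surgery variation in the outcome stays in the error term, and the confidence interval is wider than it need be. The balance part is best settled before allocation starts, since later adjustment recovers less of it.

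**Working it through.** **Inputs from the protocol.** Baseline mean 36, SD 21.6, 80% power, 0.05 (read as two-sided alpha), a 30% relative effect, 64 per group required and 100 per group enrolled (Sample size calculation); about ten surgeries and about 200 patients (Subject recruitment), so about 20 per surgery.

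**Assumed.** The share of outcome variance that lies between surgeries (ICC) is not given. I use 0.01 to 0.20.

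**1. The plan's own figure.** Reading 30% as relative to the mean of 36, the difference is 0.30 × 36 = 10.8 points, and 10.8 / 21.6 = 0.50 SD. The normal formula gives n = 2 × (1.960 + 0.842)² / 0.50² = 62.8, so 63. The t-distribution version gives 63.8, so 64. The stated 64 reproduces.

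**2. Chance imbalance.** If allocation ignores surgery, a surgery of 20 splits 14:6 or worse with probability 2 × P(Bin(20, 0.5) ≤ 6) = 0.115. For at least one of ten surgeries this is 1 − (1 − 0.115)^10 = 0.71. That treats every patient as a separate coin toss. In simulation with exact balance inside the four score bands, it is 60% to 63%.

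**3. What one such split does.** With 100 per arm, a 14:6 surgery moves the contrast by (0.14 − 0.06) = 0.08 of its surgery effect. A one-SD surgery effect is 21.6 × √0.05 = 4.8 points at ICC 0.05 and 21.6 × √0.20 = 9.7 points at ICC 0.20. The shifts are about 0.4 and 0.8 points, against a 10.8-point target.

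**4. Precision recovered.** With allocation balanced by surgery and surgery in the model, the residual SD is 21.6 × √(1 − ICC).

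| Assumed ICC | Residual SD | n per group for 80% | Power at 64 | Power at 100 |
|---|---|---|---|---|
| 0 (as planned) | 21.60 | 64 | 80.1% | 94.0% |
| 0.01 | 21.49 | 64 | 80.5% | 94.2% |
| 0.05 | 21.05 | 61 | 82.1% | 95.1% |
| 0.10 | 20.49 | 58 | 84.1% | 96.0% |
| 0.20 | 19.32 | 52 | 88.1% | 97.6% |

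**5. Validity, and whether both changes are needed.** I used a simulation of 2,000 trials per scenario with ten equal surgeries. The surgery-balanced arm of it balanced on surgery in place of score band, and the outcome was generated independently of baseline score.

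| Per group | ICC | Score-band allocation, plain t-test | Score-band allocation, surgery term | Surgery-balanced allocation, surgery term |
|---|---|---|---|---|
| 65 | 0 | 81.5% | 78.0% | 80.4% |
| 65 | 0.05 | 81.3% | 78.8% | 82.6% |
| 65 | 0.10 | 81.5% | 82.4% | 83.8% |
| 100 | 0 | 94.7% | 93.0% | 93.7% |
| 100 | 0.05 | 94.7% | 93.8% | 95.2% |
| 100 | 0.10 | 94.2% | 94.9% | 95.8% |

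The Monte Carlo standard error at 80% power is √(0.8 × 0.2 / 2000) = 0.9 points. Type I error of the plain t-test under score-band allocation stayed between 0.044 and 0.054. The surgery term on its own loses about 3 points at 65 per group when surgery explains nothing. Combined with balanced allocation, its cost is within simulation error.

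**The case against.** The strongest reply is that this is a refinement and not an error. Patients are randomised individually, so imbalance by surgery is chance, and the simulated type I error confirms that the plain t-test remains valid. Stratifying on the baseline value of the outcome is a sound choice. Stable differences, such as a consistently strict scorer, partly cancel in the before-after change described in the Summary. Calibration, central culture reading and central Cariogram entry reduce them further. Only differences between surgeries in change would remain, and the protocol gives no evidence of their size. The SD of 21.6 is also tied to the baseline score and not to change. At 100 per group power is already about 94%. All of this stands, and it limits the weight of the point.

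It does not remove the point. Calibration is stated for caries and plaque scoring, not for interviews, and a change score does not cancel surgery differences that develop over the six months.

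A reader might infer more than the protocol supports:
- **That the comparison is biased, or that 64 per group is wrong.** Neither follows. The 64 reproduces, and an SD of 21.6 may already contain between-surgery variation.
- **That each dentist gives all background dental care during the trial.** The text says only that patients are seen by their own practitioners in the surgeries. It also counts surgeries, not dentists.
- **That the 71% measures harm.** It is the chance of one lopsided surgery. The resulting shift is a fraction of a point in the examples above, and other surgeries may offset it.

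**Conclusion.** The point holds as a modest, avoidable loss of precision. Score band is the only balancing factor and the stated comparison has no surgery term, although surgery-level staff produce much of the score at both visits. A marked imbalance in at least one surgery is more likely than not under equal surgeries of 20, but its effect on the contrast is small. The gain from acting is about 0.4 to 8 power points at 64 per group and about 0.2 to 4 points at 100 per group, over assumed surgery shares of 1% to 20%. At the low end it is negligible.

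These figures rest on the assumed shares, equal surgery sizes, the 10.8-point reading of the target difference, and the planning SD applied to the analysed outcome. The change is still worth making, because it needs no extra patients or data and costs almost nothing if surgery turns out not to matter.

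**What to change.** In Randomisation, state that the statistician balances allocation on surgery as well as baseline score band. Fully crossing them gives 4 × 10 = 40 cells of about 200 / 40 = 5 patients, which is sparse. Two workable alternatives are minimisation on both factors with a random element, or small blocks within surgery with baseline score as a covariate in the analysis. The allocation is made by the statistician after baseline forms and cultures have reached the research centre, so surgery is known at that moment.

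In Data analysis, state that the comparison of the arms includes surgery as a term, for example in a linear model in place of the plain t-test. Make both changes together, because the term without balanced allocation can lose power when surgery effects are small.

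The cost is one sentence in each section, about nine degrees of freedom out of roughly 200, and a slightly more complex allocation procedure.

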To investigate the effectiveness of the approach, we will conduct an evaluator-blind randomised controlled study. Approximately 200 medical-card (proxy for low socioeconomic status) patients recruited from approximately 10 dental surgeries in Ireland will be randomly assigned to test and control groups. The caries risk profile of all subjects will be assessed using Cariogram at baseline and at six months. Once weekly for 24 weeks, the Test group will receive personalised educational text messages on caries prevention while the Control group receives non-personalised educational text messages. The average change in "chance to avoid new cavities" as measured by Cariogram before and after the intervention between the test and control groups will be compared using a two-sample two-sided t-test.

If the electronic personalised education system (EPES) for caries prevention proves successful, it represents a ground-breaking approach to reducing caries risk and building patient engagement in those with greatest need, adopting modern technologies to promote regular check-ups and better dental health. Furthermore, the concept could be adapted and applied to other lifestyle related diseases with individual variability.

Introduction

Although many studies have shown lower socioeconomic groups have a greater burden of dental disease than higher socioeconomic groups (Petersen, Bourgeois, Ogawa, Estupinan-Day, & Ndiaye, 2005), studies have not shown the particular individual variability of caries (tooth decay) risk within the lower socioeconomic groups. Caries risk may vary from person to person and may change during a person's lifetime; if individual variability exists, then personalised caries prevention and management are imperative. The literature suggests that providing caries prevention advice without reference to the individual's specific risk factors is not effective in achieving long-term behaviour change (Kay & Locker, 1998; Yevlahova & Satur, 2009).

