[name] has been conducting a questionnaire survey on personalised caries prevention

in a Japanese population as her PhD project. That questionnaire has been adapted for use in this project. A Japanese non-profit organization (NPO), of which [name] is the President, has adapted Rapport Builder® for sending oral health messages to its members. This project will work on the adapted version of Rapport Builder® (Figure 2).

Figure 2. Example of a text message to be used in this study. Simple messages are delivered weekly in a humorous manner to engage the attention of the target audience.

Hi! Prevent tooth decay by making smart & healthy food choices: foods & drinks high in sugar can lead 2 tooth decay & weight gain. Eat smart, stay healthy!

Study methodology

This project is a randomised controlled study. The null hypothesis is that no difference exists between the group receiving EPES and the group receiving non-personalised information.

The innovativeness of this project made it difficult to set the intervention interval. We considered an interval of more than six months, however we wished to maintain subject engagement and to assess the study outcomes and innovativeness. In addition, the Cariogram manual suggests re-assessment in six months for high-risk patients.

Train dental professionals

Baseline exam

Culture of bacteria Randomisation

Test group
Personalised txt messages weekly

Control group
Non-personalised txt messages weekly

Follow-up exam

The project process is set out below (Figure 3).

Figure 3. Process chart. Orange boxes indicate activities carried out at the Oral Health Services Research Centre (OHSRC); green boxes indicate activities at dental surgeries.

Culture of bacteria
Data analysis

Sample size calculation

To estimate the sample size, we conducted a power calculation based on previous Cariogram studies. Where the average baseline Cariogram "chance to avoid new cavities" score is 36, with a mean between-subject standard deviation of 21.6, a sample of 64 subjects per group is required. This will provide an 80% power with a margin of error of 0.05, to detect a "chance to avoid new cavities" of at least 30% relative to the control group over the 6-month duration of the study.

To ensure adequate numbers in each group at six months to permit appropriate analysis, and minimising the risk of type II error, 100 subjects will be entered in each group at baseline.

Subject recruitment

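### The main Cariogram comparison is worded as change in one section and as average in another, and both fix an unadjusted t-test although allocation is stratified on the baseline score

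*Protocol*

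**What the plan says.** The Protocol describes the main comparison in two places.

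- **Summary:** "The average change in 'chance to avoid new cavities' as measured by Cariogram before and after the intervention" is to be compared between the arms by a two-sided t-test.
- **Data analysis:** "The average of 'chance to avoid new cavities' as measured by Cariogram as well as the seven risk factors before and after the intervention", and these "between the test and control groups will be compared using a two-sample two-sided t-test". The word for change is absent here.

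Neither place mentions a covariate or a stratum term.

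The Randomisation section says: "The subjects will be stratified for 'chance to avoid new cavities' by quartiles". It lists four bands (0–20, 21–40, 41–60 and 61–100%), and subjects are then "randomly allocated to Test or Control group by the statistician". No block size or other balancing method is given.

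The Sample size calculation section works from the score itself: "Where the average baseline Cariogram 'chance to avoid new cavities' score is 36", "with a mean between-subject standard deviation of 21.6". It requires 64 per group for 80% power at 0.05 and a 30% relative difference, and enters 100 per group. It gives no SD of change and no correlation between baseline and six months.

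**The concern.** A t-test on the six-month score and a t-test on change have different variances, and they can reach different conclusions from the same data. The Data analysis sentence does not settle which is meant. The sample size does not settle it either: an SD of 21.6 for the score suits a six-month comparison, and suits a change comparison only if the baseline to six-month correlation is exactly 0.5.

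The second matter is efficiency. Allocation is stratified on the baseline value of the outcome, yet the named test makes no allowance for that. When a prognostic variable is balanced by design and then left out of the model, the calculated standard error includes variation that the design has already removed. At stake are some power and an avoidable choice between analyses on the outcome that carries the sample size.

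**Working it through.** **Inputs from the Protocol.** Baseline mean 36; SD 21.6; relative difference 30%; power 80%; two-sided 0.05; 64 per group required; 100 per group entered.

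**Assumptions (not in the Protocol).** Baseline to six-month correlation ρ of 0.3, 0.5 or 0.7; SD of 21.6 at both times; normal scores, not truncated at 0 or 100. The simulations also assume permuted blocks of 4 within the four bands, unless stated otherwise.

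**1. The Protocol's own figure.** The difference is 0.30 × 36 = 10.8 points, and 10.8 / 21.6 = 0.5 SD. Then n = 2(1.96 + 0.84)² / 0.5² ≈ 63 per group. The t distribution gives 63.8, hence 64. The stated 64 is reproduced, for an unadjusted comparison of six-month scores.

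**2. SD under each analysis.**

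- Six-month score: 21.6 at any ρ.
- Change: 21.6 × √(2(1 − ρ)) = 25.6, 21.6 and 16.7 at ρ = 0.3, 0.5 and 0.7.
- ANCOVA residual: 21.6 × √(1 − ρ²) = 20.6, 18.7 and 15.4.

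**3. Sample size and power from these SDs (normal formula).**

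| | ρ = 0.3 | ρ = 0.5 | ρ = 0.7 |
|---|---|---|---|
| n per group for 80%: six-month t | 63 | 63 | 63 |
| n per group for 80%: change t | 88 | 63 | 38 |
| n per group for 80%: ANCOVA | 58 | 48 | 33 |
| Power at 64: six-month t | 81% | 81% | 81% |
| Power at 64: change t | 67% | 81% | 96% |
| Power at 64: ANCOVA | 84% | 90% | 98% |
| Power at 100: six-month t | 94% | 94% | 94% |
| Power at 100: change t | 85% | 94% | 99.5% |
| Power at 100: ANCOVA | 96% | 98% | 99.9% |

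**4. Why the t-tests become conservative under balance.** The baseline explains a share ρ² of the variance of the six-month score: 0.09, 0.25 and 0.49. It explains (1 − ρ)² / (2(1 − ρ)) = (1 − ρ)/2 of the variance of change: 0.35, 0.25 and 0.15. If the design balanced the baseline perfectly, the t-test would in effect use a critical value of 1.96 / √(1 − share).

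- Six-month t: 2.05, 2.26 and 2.74, so a true error of about 4.0, 2.4 and 0.6%.
- Change t: 2.43, 2.26 and 2.13, so about 1.5, 2.4 and 3.4%.

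Four bands balance the baseline only in part, so the real figures should lie between these limits and 5%.

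**5. Simulation, 64 per arm, blocks of 4 within bands (range over repeated runs).**

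| | ρ = 0.3 | ρ = 0.5 | ρ = 0.7 |
|---|---|---|---|
| Type I error: six-month t | 4.0–4.4% | 2.6–3.0% | 1.0–1.2% |
| Type I error: change t | 1.8–2.2% | 2.7–3.1% | 3.4–4.2% |
| Type I error: ANCOVA | about 5% | about 5% | about 5% |
| Power: six-month t | 80–82% | 82–83% | 86–87% |
| Power: change t | 68–70% | 83% | 96% |
| Power: ANCOVA | 83–85% | 90% | 97–98% |

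With a true effect of 10.8 points, the two t-tests disagreed on significance in 15, 10 and 10% of simulated trials.

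**6. Without balance within bands.** Under simple randomisation, the simulated type I error of both t-tests was between 4.2 and 5.3%. The conservatism disappears or nearly so.

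**7. With more completers (simulation).** Power of six-month t / change t / ANCOVA at 100 per arm was 94/88/96% at ρ = 0.3, 96/96/98% at 0.5 and 98/99/over 99% at 0.7. At 80 per arm (an assumed 20% loss) it was 90/80/91%, 91/91/96% and 94/99/99%.

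**The case against.** Five points can be made for the plan.

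- **The two sections may mean the same thing.** The Data analysis sentence keeps the before-and-after phrase of the Summary and may simply be a loose way of saying change. A reader might infer two rival endpoints in open contradiction. The text does not go that far, because no section names the six-month score alone as the outcome. What stands is that the sentence does not define one test.
- **A change score uses the baseline.** A reader might infer that both versions ignore it. That is not so for change, which subtracts it. At ρ = 0.7 the change t-test is within about 2 points of ANCOVA in power.
- **The conservatism is conditional.** A reader might infer that the standard errors are wrong whatever happens. They are too large only if allocation is balanced within bands. Balance is the usual purpose of stratifying, but the Protocol describes no method that secures it.
- **The plan has a reserve.** With 100 entered per arm, the simulated 68–70% for the change test needs 36% attrition and ρ near 0.3 together. This objection stands.
- **An analysis plan could add covariates.** That holds for detail left open. Here the Protocol itself fixes the unadjusted test twice, so adding a covariate would depart from its text.

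A reader might also infer that surgery must be in the model because each practice scores its own patients. The documents do not support this. Practices record clinical inputs after calibration, but bacterial slides are read at the research centre, and a study team member enters the data and generates the Cariogram results. Allocation is by individual, and none of the calculations here includes a surgery effect.

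**Conclusion.** The point holds as one of wording and efficiency. The main comparison should be defined once, and the unadjusted t-test is a weaker choice than a baseline-adjusted analysis. Neither t-test is biased or inflates false positives, and the stated 64 per group is correct for a six-month comparison.

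The size depends on a correlation that the Protocol does not give. At 64 per arm, ANCOVA gains about 3 points over the six-month t-test at ρ = 0.3, 7 at 0.5 and 11 at 0.7. Over the change t-test it gains about 15, 7 and 1 points. If all 100 per arm complete, the simulated gain over the six-month test is about 2 points or less; over the change test it is 8 points at ρ = 0.3 and 2 or less from 0.5 upwards. The type I error of 1 to 4% applies only under balanced allocation within bands.

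This should be fixed as a nearly free improvement. It is not a fault that invalidates the trial.

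**What to change.** State one analysis, in the same words, in the Summary and in Data analysis: ANCOVA of the six-month Cariogram score on arm, with the continuous baseline score as covariate and, optionally, the stratum. Report the adjusted mean difference with its 95% confidence interval. Keep the t-test only as a sensitivity analysis, and say whether it uses change or the six-month score.

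The cost is a wording change in two sections, best made before unblinded data are seen. Every randomised subject already has a baseline score, because stratification needs it. No new data and no more patients are required.
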